3.5.3. Vital Signs

Supine blood pressure (BP) and pulse rate (PR) will be measured at times specified in the SoA given in the protocol.

For both periods, the baseline measurement is the predose measurement on Day 1 in each period.

3.5.4. Electrocardiograms

QT interval, QTcF, PR, QRS and heart rate (HR) will be recorded at each assessment time indicated in the SoA given in the protocol. QTcF will be derived using Fridericia's heart rate correction formula:

$$\text{QTcF} = \text{QT} / (\text{RR})^{1/3} \text{ where RR} = 60/\text{HR} \text{ (if not provided)}$$

For both periods, the baseline measurement is the predose measurement on Day 1 in each period.

4. ANALYSIS SETS (POPULATIONS FOR ANALYSIS)

Data for all participants will be assessed to determine if participants meet the criteria for inclusion in each analysis population prior to releasing the database and classifications will be documented per standard operating procedures.

Participant Analysis Set	Description
Enrolled/Randomly assigned to study intervention	“Enrolled” means a participant’s, or their legally authorized representative’s, agreement to participate in a clinical study following completion of the informed consent process and screening. A participant will be considered enrolled if the informed consent is not withdrawn prior to participating in any study activity after screening. Potential participants who are screened for the purpose of determining eligibility for the study, but do not participate in the study, are not considered enrolled, unless otherwise specified by the protocol.
Safety Analysis Set	All participants who take at least 1 dose of study intervention. Participants will be analyzed according to the product they actually received.
PK Concentration Set	All participants who take at least 1 dose of study intervention and in whom at least 1 concentration value is reported.
PK Parameter Set	All participants who take at least 1 dose of study intervention and in whom at least 1 of the PK parameters of interest are reported. Should vomiting occur after administration of PF-07081532, the resulting PK parameters from that participant from the corresponding period may be excluded.

5. GENERAL METHODOLOGY AND CONVENTIONS

Final analysis will be performed after study participant data set release following last participant last visit.

5.1. Hypotheses and Decision Rules

No statistical hypothesis will be tested in this study.

5.2. General Methods

5.2.1. Analyses for Binary/Categorical Endpoints

For binary or categorical variables, number of participants, numbers and percentages of participants meeting the categorical criteria will be presented in accordance with the Clinical Data Interchange Standards Consortium and Pfizer Standards (CaPS).

5.2.2. Analyses for Continuous Endpoints

For continuous variables, the data will be summarized using the number of participants, mean, median, standard deviation (SD), minimum, and maximum in accordance with the CaPS. For appropriate PK parameters, geometric mean and geometric coefficient of variation (%CV) will also be summarized.

5.3. Methods to Manage Missing Data

5.3.1. Pharmacokinetic Data

Methods to handle missing PK data are described below.

Concentrations Below the Limit of Quantification:

In all data presentations (except listings), concentrations below the limit of quantification (BLQ) will be set to zero. In listings, BLQ values will be reported as “<LLQ”, where LLQ will be replaced with the value for the lower limit of quantification.

Deviations, Missing Concentrations and Anomalous Values:

In summary tables and plots of median profiles, statistics will be calculated having set concentrations to missing if 1 of the following cases is true:

1. A concentration has been collected as ND (ie, not done) or NS (ie, no sample).
2. A deviation in sampling time is of sufficient concern or a concentration has been flagged anomalous by the pharmacokineticist.

Note that summary statistics will not be presented at a particular time point if more than 50% of the data are missing.

An anomalous concentration value is one that, after verification of bioanalytical validity, is grossly inconsistent with other concentration data from the same individual or from other

participants. For example, a BLQ concentration that is between quantifiable values from the same dose is considered as anomalous. Anomalous concentration values may be excluded from PK analysis at the discretion of the PK analyst.

PK Parameters:

Actual PK sampling times will be used in the derivation of PK parameters. If a PK parameter cannot be derived from a participant's concentration data, the parameter will be coded as NC (ie, not calculated). (Note that NC values will not be generated beyond the day that a participant discontinues).

In summary tables, statistics will not be presented for a particular treatment group if more than 50% of the data are NC. For statistical analyses, PK parameters coded as NC will also be set to missing.

If an individual participant has a known biased estimate of a PK parameter (due for example to a dosing error or an unexpected event such as vomiting before all the compound is adequately absorbed from the gastrointestinal tract), this will be footnoted in summary tables and will not be included in the calculation of summary statistics or statistical analyses. For instance, if a participant has a vomiting event post dose that is within a duration of time that is 2-times the derived median T_{max} for the population for the administered treatment, then the pharmacokineticist should consider the exclusion of the PK concentration data collected following the initial vomiting event in that treatment period and the PK parameter data reported for that treatment period from the datasets used to calculate summary statistics or statistical analyses.

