7. INTERIM ANALYSES

No formal interim analysis will be conducted for this study. As this is an open-label study, the sponsor may conduct unblinded reviews of the data during the course of the study for the purpose of safety assessment, facilitating PK/PD modeling, and/or supporting clinical development.

Final analysis will follow the official database release. As this will be an open-label study, there is no formal unblinding of the randomization code.

APPENDICES

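### Does leaving the vomiting exclusion in SAP 5.3.1 to an unmasked pharmacokineticist put the Test/Reference ratio at risk?

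*SAP*

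**What the plan says.** SAP 5.3.1 (PK Parameters) begins with a firm rule: an estimate known to be biased, for instance by a dosing error or by vomiting before absorption is adequate, is footnoted and left out of summary statistics and statistical analyses. Vomiting is then worked as an example. If it occurs "within a duration of time that is 2-times the derived median" Tmax for the treatment given, "then the pharmacokineticist should consider the exclusion of the PK concentration data collected following the initial vomiting event", together with "the PK parameter data reported for that treatment period from the datasets used to calculate summary statistics or statistical analyses". SAP 4 and protocol 9.2 also word the vomiting exclusion from the PK Parameter Set as permitted, not required.

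For single concentrations, SAP 5.3.1 says: "Anomalous concentration values may be excluded from PK analysis at the discretion of the PK analyst". A value counts as anomalous only "after verification of bioanalytical validity". The example is a result below the quantification limit lying between quantifiable ones.

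On timing, SAP 4 has membership of the analysis sets assessed "prior to releasing the database and classifications will be documented per standard operating procedures", and SAP 5 says: "Final analysis will be performed after study participant data set release following last participant last visit". SAP 7 adds that "the sponsor may conduct unblinded reviews of the data during the course of the study", for safety, PK/PD modelling or development purposes. Under protocol 6.4.3 sponsor staff know the assignments.

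SAP 6.1 plans further analyses only if the residuals look poor: other transformations, or removal of outliers. SAP 6.3.1 lists every concentration with its actual time.

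**The concern.** The product of this study is a Test/Reference ratio with a 90% CI from about 14 to 20 people, and protocol 4.2 says it will help choose the Formulation B dose for later studies. At that size each profile counts. The SAP gives a numeric window for vomiting but no fixed decision once the window is met, and the decision may be taken by someone who knows which formulation the profile belongs to.

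The choice is a real one. Protocol 4.3 reports that earlier vomiting generally followed Cmax and had no apparent effect on exposure. A window of twice the median Tmax can therefore catch profiles that are perfectly valid, and two competent analysts could decide differently. The conditional analyses in SAP 6.1 only remove more data or change the scale; none puts excluded data back. A reader would see that a period had gone, but not what its removal did to the ratio.

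**Working it through.** **1. The plan's own precision figure.** Inputs from protocol 9.5: n=14, within-participant SD 0.291 (lnAUC) and 0.171 (lnCmax), 90% CI, 80% coverage. Log half-width = t(0.95, 12) × SD × √(2/14) × √(chi-square(0.80, 12)/12). For AUC: 1.782 × 0.291 × 0.378 × 1.148 = 0.225. At a ratio of 100% this gives 79.85-125.23%, as tabulated. All 14 rows of the table reproduce.

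**2. Between-participant SD.** The documents do not state one. Protocol 4.2 gives an inter-participant geometric CV for AUCinf of 28-34% (fed, described as comparable to fasted). Log SD = √ln(1+CV²), which is 0.275 to 0.331.
- Read as total variability: √(0.331² − 0.291²) = 0.157 at the top. At the bottom 0.275 is below 0.291, so the between-participant SD is set to 0.
- Read as purely between-participant: 0.275 to 0.331.

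**3. Influence of one ordinary excluded period.** Take m participants per sequence (7 or 10). The mixed model keeps the participant's other period.
- Lower limit (between SD 0): the treatment estimate gives each of the four sequence-by-period means weight one half, so the SD of the shift is SD/(2√(m(m−1))).
- Upper limit (the other period carries no information): the same, multiplied by √2.
- Median absolute shift = 0.6745 × that SD.

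For AUC, n=14: 0.291/(2√42) = 0.0225, median 0.0151; upper limit 0.0318, median 0.0214. For n=20: 0.291/(2√90) = 0.0153, median 0.0103; upper limit 0.0217, median 0.0146. In round terms this is 1.5-2.1% and 1.0-1.5%. For Cmax, 0.171 in place of 0.291 gives about 0.9-1.3% and 0.6-0.9%.

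A simulation of the SAP model fitted by REML (20,000 trials per setting), AUC:

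| Between SD | n=14 median (90th pct) | n=20 median (90th pct) |
|---|---|---|
| 0 | 1.54% (3.79%) | 1.06% (2.57%) |
| 0.157 | 1.74% (4.18%) | 1.16% (2.88%) |
| 0.275 | 1.89% (4.59%) | 1.29% (3.13%) |
| 0.331 | 1.97% (4.78%) | 1.31% (3.20%) |

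Over these settings the standard error grows by 3.4-4.8% at n=14 and 2.3-3.2% at n=20.

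**4. Against the planned interval.** At n=14: 0.0151/0.225 = 7% and 0.0214/0.225 = 10% of the log half-width.

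**5. What a refit with the period retained would show.** If vomiting truly cost a fraction of that period's AUC (assumed 20% or 50%), keeping it moves the ratio by a factor of 0.8^(1/14) or 0.5^(1/14), that is 1.6% or 4.8%, at n=14. At n=20 it is 1.1% or 3.4%. These shifts are as large as those in step 3, so a gap between the two runs would not tell a doubtful exclusion from a correct one.

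**6. Safeguards already written.** Known bias means mandatory exclusion and a footnote (SAP 5.3.1). Set membership is documented before release (SAP 4), and the final analysis comes after it (SAP 5). The exclusion applies to the datasets behind summaries and models, while SAP 6.3.1 still lists all concentrations, so a dropped profile can be recomputed.

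**The case for a change.** The best case for acting is that the remedy is cheap: record each decision and its reason on a listing without treatment codes, and refit the same model with excluded data kept. If nothing is excluded it costs nothing. If two valid periods were flagged, the AUC ratio could span a median of 3.5-3.8% (n=14) or 2.4-2.6% (n=20) over the four keep-or-drop choices, with the protocol's CV read as total variability. That is more than a rounding matter.

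Some of this stands. No planned run retains excluded data. Anomalous single values fall outside the set definitions, so the pre-release step in SAP 4 does not clearly cover them, and the reviews allowed by SAP 7 could come before a decision.

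Much does not. Masking one listing protects little when sponsor staff hold the assignments and the window itself uses the median Tmax of the treatment given; a pre-programmed flag would help only in part. Keeping every anomalous value is worse than dropping it. In the SAP's own example it would place an unquantifiable result in mid-profile, and the SAP has no rule for that in the logarithmic part of the trapezoidal calculation. Dropping such a value cannot alter Cmax. A fixed rule has its own cost: automatic exclusion would lose the valid profiles that protocol 4.3 leads one to expect, and automatic retention would keep profiles with real absorption loss.

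**Conclusion.** No change is needed. Followed as written, the plan gives a sound ratio and CI. The discretion is confined to judging whether a flagged profile is biased. That is ordinary pharmacokinetic judgement, exercised under a mandatory exclusion rule and left visible in footnotes and listings. It is a fair trade-off between losing valid profiles and keeping spoiled ones.

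The size supports this. One ordinary excluded period moves the AUC ratio by a median of about 1.5-2.1% (n=14) or 1.0-1.5% (n=20), in either direction. SAP 5.1 tests no hypothesis and there is no margin to cross. Protocol 4.3 reports vomiting at 100 and 200 mg and expects acceptable gastrointestinal tolerability at 80 mg, so the number of such exclusions may be zero. Enrolling about 20 to secure 14 evaluable participants leaves room for a few.

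The figures assume balanced sequences, the planning SDs in protocol 9.5 and a single excluded period that is otherwise typical. They show influence; nothing in the documents suggests a bias towards either formulation. Should an exclusion occur and its effect be questioned, the analyst can refit the same model from the listed concentrations, with the caution that a true absorption loss would also shift that result.

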5.3.2. Safety Data

Missing values in standard summaries of AEs, laboratory data, vital signs, and ECGs will be imputed according to CaPS.

6. ANALYSES AND SUMMARIES

6.1. Primary Endpoints

AUC_{inf} (if data permit), AUC_{last} and C_{max} will be summarized by treatment group and will include the set of summary statistics as specified in [Table 4](#).

For the evaluation of relative bioavailability, *natural log transformed AUC_{inf} (if data permit), AUC_{last} and C_{max} will be analyzed using a mixed effect model with sequence, period and treatment as fixed effects and participant within the sequence as a random effect. Estimates of the adjusted mean differences (Test-Reference) and corresponding 90% CIs will be obtained from the model. The adjusted mean differences and 90% CIs for the differences will be exponentiated to provide estimates of the ratio of adjusted geometric means (Test/Reference) and 90% CI for the ratios. Formulation A (PF-07081532 20 mg + 60 mg) will be the Reference treatment while Formulation B (PF-07081532 80 mg) will be the Test treatment.*

For AUC_{inf} , AUC_{last} and C_{max} , a listing of the individual participant ratios (Test/Reference) will be provided. Box and whisker plots for AUC_{inf} , AUC_{last} and C_{max} , will be plotted by treatment and overlaid with geometric means.

Residuals from the model will be examined for normality and the presence of outliers via visual inspection of plots of residuals vs predicted values and normal probability plots of residuals but these will not be included in the CSR. If there are major deviations from normality or outliers then the effect of these on the conclusions will be investigated through alternative transformations and/or analyses excluding outliers. Justification for any alternative to the planned analysis will be given in the report of the study.

6.2. Secondary Endpoints

Analyses and summaries of safety data are described in [Section 6.6](#).

6.3. Other Endpoints

6.3.1. PK Concentration

The plasma concentrations of PF-07081532 will be listed and descriptively summarized by nominal PK sampling time and treatment. Individual participant, as well as mean and median profiles of the plasma concentration time data will be plotted by treatment using actual (for individual) and nominal (for mean and median) times respectively. Mean and median profiles will be presented on both linear and semi-log scales.

Presentations of concentrations will include:

- A listing of all concentrations sorted by participant ID, treatment and nominal time postdose. The concentration listing will also include the actual times. Deviations from the nominal time will be given in a separate listing.
- A summary of concentrations by treatment and nominal time postdose, where the set of statistics will include n, mean, median, SD, %CV, minimum, maximum and the number of concentrations above the LLQ.
- Median concentrations time plots (on both linear and semi-log scales) against nominal time postdose by treatment (all treatments on the same plot per scale, based on the summary of concentrations by treatment and time postdose).
- Mean concentrations time plots (on both linear and semi-log scales) against nominal time postdose by treatment (all treatments on the same plot per scale, based on the summary of concentrations by treatment and time postdose).
- Individual concentration time plots by treatment (on both linear and semi-log scales) against actual time postdose (there will be separate spaghetti plots for each treatment per scale).

- Individual concentration time plots by participant (on both linear and semi-log scales) against actual time postdose [there will be separate plots for each participant (containing all treatments) per scale].

6.3.2. PK parameter

The PK parameters will be listed and summarized descriptively by treatment group in accordance with Pfizer data standards on the PK Parameter Analysis Set, as data permit. Missing values will be handled as detailed in [Section 5.3.1](#). Each PK parameter will be summarized by treatment group and will include the set of summary statistics as specified in Table 4.

Table 4. PK Parameters to be Summarized Descriptively by Treatment

Parameter	Summary Statistics
AUC _{inf} , AUC _{last} , C _{max} , CL/F, V _z /F	N, arithmetic mean, median, SD, %CV, minimum, maximum, geometric mean and geometric %CV
T _{max}	N, median, minimum, maximum
t _½	N, arithmetic mean, median, SD, %CV, minimum, maximum

Supporting data from the estimation of t_½ and AUC_{inf} will be listed by analyte and group: terminal phase rate constant (k_{el}); goodness of fit statistic from the log-linear regression (r²); the percent of AUC_{inf} based on extrapolation (AUC_{extrap} %); and the first, last, and number of time points used in the estimation of k_{el}. This data may be included in the clinical study report.

6.4. Subset Analyses

There are no planned subset analyses.

6.5. Baseline and Other Summaries and Analyses

6.5.1. Demographic Summaries

Demographic characteristics will be summarized for enrolled population in accordance with the CaPS.

6.5.2. Study Conduct and Participant Disposition

Participants evaluation groups will show end of study participant disposition. Frequency counts will be supplied for participant discontinuation(s) by treatment. Data will be reported in accordance with the CaPS.

6.5.3. Study Treatment Exposure

Study treatment exposure will be listed.

6.5.4. Concomitant Medications and Nondrug Treatments

All prior and concomitant medication(s) as well as non-drug treatment(s) will be reported in the listings.

6.6. Safety Summaries and Analyses

All safety analyses will be performed on the Safety Analysis Set.

Safety data will be presented in tabular and/or graphical format and summarized descriptively, where appropriate.

6.6.1. Adverse Events

Adverse events will be reported in accordance with the CaPS.

Participant discontinuations due to adverse events will be detailed by treatment. Data will be reported in accordance with the CaPS.

6.6.2. Laboratory Data

Laboratory data will be listed and summarized by treatment in accordance with the CaPS.

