**SoA-Table 1. Study Schedule of Assessment**

Visit Identifier Abbreviations used in this table may be found in Appendix 10 .	Screening	Periods 1 and 2					ET	Follow -Up	Notes
Days Relative to Day 1	Day -28 to Day -2	Day -1 (Period 1 Only)	Day 1	Day 2	Day 3	Day 4	Day 5		28-35 days
Hours After Dose			0	48	72	96			
Informed consent	X								
Demography	X								
COVID-19 assessment		See Notes							

• All screening should be done <math>\leq</math>28 days before the first dose.

• Day relative to start of study intervention (Day 1).

• Follow-up may occur via telephone contact and must occur 28 to 35 days after administration of the final dose of study intervention.

Review of eligibility criteria	X	X							
Inpatient stay at Clinical Research Unit		X	→	→	→	→	X		
Medical history	X	X							

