**SoA-Table 1. Study Schedule of Assessment**

Visit Identifier Abbreviations used in this table may be found in Appendix 10 .	Screening	Periods 1 and 2					ET	Follow -Up	Notes
		Day -1 (Period 1 Only)	Day 1	Day 2	Day 3	Day 4			
Days Relative to Day 1	Day -28 to Day -2							28-35 days	
 
All screening should be done <math>\leq</math>28 days before the first dose.
 
Day relative to start of study intervention (Day 1).
 
Follow-up may occur via telephone contact and must occur 28 to 35 days after administration of the final dose of study intervention.
 

Hours After Dose		0	48	72	96				
Blood samples for:									
Clinical laboratory tests after 4-hour fast	X	X					X	X	
 
See Appendix 2 for details of clinical laboratory tests
 
Day 5: Procedures at discharge (Period 2) only.
 

FSH (postmenopausal females only), HBsAg, HBcAb, HCVAb, calcitonin	X								
HIV	X								
Pregnancy test (WOCBP only)	X	X					X	X	
 
Day 5: Procedures at discharge (Period 2) only.
 

CCI			■					■	[REDACTED]
CCI			■					■	[REDACTED]

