## 4. STUDY DESIGN

### 4.1. Overall Design

This is a randomized, open-label, single dose, 2-period, 2-sequence, crossover study. Participants will be screened for participation in this study within 28 days before dosing in Period 1 to confirm that they meet the inclusion/exclusion criteria for this study. A minimum washout of 6 days between the single 80 mg doses (80 mg immediate release tablet for Formulation B, 20 mg immediate release tablet + 60 mg immediate release tablet for Formulation A) administered in each period will be employed. The expected duration of participation from Screening to the Follow-up telephone contact will be approximately 10 weeks.

Approximately 20 participants will be enrolled to ensure at least 14 evaluable participants with PK data.

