3.5.1. Adverse Events

Any adverse events occurring following start of treatment will be considered as treatment emergent adverse event (TEAE). Events that occur during follow-up within the lag time of up to 35 days after the last dose of study intervention will be counted as treatment emergent and attributed to the last treatment taken. The time period for collecting AEs (“active collection period”) for each participant begins from the time the participant provides informed consent.

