3.5.2. Laboratory Data

Safety laboratory tests will be performed as described in the protocol. To determine if there are any clinically significant laboratory abnormalities, the haematological, clinical chemistry (serum) and urinalysis safety tests will be assessed against the criteria specified in the sponsor reporting standards. The assessment will not take into account whether each participant's baseline test result is within or outside the laboratory reference range for the particular laboratory parameter.

For both periods, the baseline measurement is the predose measurement on Period 1 Day -1.

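### Laboratory data are to be summarised by treatment, but a completer's only scheduled post-dose draw follows both formulations, so the columns cannot isolate either one

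*SAP*

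**What the plan says.** - SAP 6.6.2 consists of one sentence: "Laboratory data will be listed and summarized by treatment in accordance with the CaPS". It gives no rule for deciding which treatment a draw belongs to.
- Protocol SoA-Table 1 marks clinical laboratory tests at screening, Day -1, Day 5 and early termination; Days 1 to 4 are blank. The Day -1 column heading begins "Day -1 (Period 1 Only", and the note on the Day 5 draw is "Day 5: Procedures at discharge (Period 2) only".
- SAP 3.5.2 sets the laboratory baseline: "For both periods, the baseline measurement is the predose measurement on Period 1 Day -1".
- Vital signs are treated differently. SAP 3.5.3 says "For both periods, the baseline measurement is the predose measurement on Day 1 in each period", and SAP 3.5.4 uses the same rule for ECGs.
- Protocol 4.1 specifies "A minimum washout of 6 days between the single 80 mg doses".
- Two statements elsewhere concern attribution, but neither is written for laboratory results. SAP 3.5.1 says that adverse events arising in follow-up "will be counted as treatment emergent and attributed to the last treatment taken". SAP 4 says of the Safety Analysis Set: "Participants will be analyzed according to the product they actually received".

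**The concern.** Side-by-side formulation columns in a crossover report invite the reader to assume that each participant contributed a result after each formulation. The laboratory schedule does not provide that. A completer has no laboratory value that reflects the first formulation alone. The value taken after the second formulation is compared with a baseline that precedes both doses, so any change from baseline spans both.

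If an abnormality arose after the first formulation and persisted, the table could place it under the second, and nothing scheduled would show otherwise. SAP 3.5.2 also assesses abnormalities without regard to whether the baseline was already out of range, so an abnormality present before any dosing could appear under a formulation as well.

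At stake is the reading of a named secondary endpoint, clinical laboratory abnormalities (Protocol 3). The PK comparison is not at stake.

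**Working it through.** The plan gives no figure on this point, so the check is one of timing, a count of draws, and what the resulting data can identify.

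**1. Timing of the post-dose draw.** The second dose is at least 6 days after the first (Protocol 4.1). Day 5 is 96 hours after dosing, or 4 days (SoA-Tables 1 and 2). The Period 2 Day 5 draw is therefore 4 days after dose 2 and at least 6 + 4 = 10 days (240 hours) after dose 1.

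**2. Scheduled laboratory draws between the doses.**
- Period 1, Days 1 to 4: none marked.
- Period 1, Day 5: none, because the draw is limited to Period 2.
- Period 2, Day -1: none, because that column applies to Period 1 only.

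Total: 0. The laboratory row has lost a cell in the extracted text, so its last mark might be read as early termination or as follow-up. For a completer this does not matter, because follow-up also comes after both doses.

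**3. What the scheduled results can identify.** Protocol Table 3 plans 10 participants per sequence.

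| Sequence | First formulation | Last formulation before the draw | Scheduled completer result after one formulation alone |
|---|---|---|---|
| 1 | A | B | none |
| 2 | B | A | none |

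There are two ways to place the single result.
- *Under the last formulation.* Let s = 0 for Sequence 1 and s = 1 for Sequence 2, and let L = 1 if the last formulation is B. Then L = 1 - s for every completer. The columns for intercept, sequence and last formulation are linearly dependent (intercept = s + L). For 20 completers the design matrix has rank 2 of 3, and the correlation of s with L is -1.0. Replacing sequence by the formulation taken first gives the same rank, 2 of 3.
- *Under both formulations.* The same values enter each column, so for scheduled completer results the two columns are identical.

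**4. Comparison with a draw in each period.** If each period had a post-dose draw, the matrix for intercept, sequence, period and treatment would have rank 4 of 4. The limitation therefore comes from the laboratory schedule and not from the crossover itself. This is an illustration; no added draw is proposed.

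**5. Results that do follow one formulation.** A participant who leaves before dose 2 may have an early-termination draw (Protocol 7.2), and unscheduled tests are allowed at any time (Protocol 8.3.4). These are the only single-formulation results. They arise from withdrawal or from a perceived safety issue, so they are not systematic.

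**The case against.** *CaPS may settle the attribution.* The standard is not among the documents, so the exact layout of the table is unknown. That is a fair limit on what can be said about column contents. It does not rescue the by-treatment summary, because no reporting convention can turn one draw taken after both doses into a result for one formulation.

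*Sequences are randomised and there is a washout.* If nothing in the laboratory values carried over from dose 1, comparing the sequences at Period 2 Day 5 would be a legitimate unpaired comparison of the last formulation. This is the strongest point, but it depends on a condition that the plan cannot check. The documents state no duration of laboratory effect, and no laboratory value is scheduled before dose 2. Vital signs and ECGs do have such a value.

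*The practical risk is low.* This stands. Protocol 2.2.4.1 reports no clinically significant laboratory trend with increasing dose in two completed studies, which tested single doses up to 200 mg and multiple doses up to 180 mg daily. The safety objective in Protocol 3 is not worded as a comparison of formulations. Clinically significant laboratory changes are also recorded as adverse events and assessed individually for causality.

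*The listings already help.* This stands in part. Laboratory data are listed as well as summarised, and SAP 6.5.3 lists treatment exposure, so a careful reader could recover sequence and last treatment. The summary table would still carry a formulation label that the data cannot support.

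**Conclusion.** The concern holds as a minor error in the planned presentation. For scheduled results in completers, a by-treatment laboratory summary cannot separate the formulations: it is either fully aliased with sequence and prior exposure, or it repeats the same values in both columns. This rests only on the Schedule of Activities and the minimum interval between doses.

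Three stronger readings are tempting, and the documents do not support them.
- *That the B column would hold only Sequence 1 completers and the A column only Sequence 2 completers, with nobody in both.* The last-treatment rule in SAP 3.5.1 covers follow-up adverse events only. The Safety Analysis Set definition does not select the last product, because a completer received both. Early-termination or unscheduled results could add other participants to either column.
- *That the error can be sized in percentage points.* Dividing one supposed abnormality by different column sizes measures no bias. The documents give no event rate or duration of effect. Completer numbers are not fixed either: enrolment is approximate, Protocol 9.5 allows replacement, and the planned minimum of 14 counts PK-evaluable participants, not completers.
- *That laboratory effects do carry over.* Nothing in the documents shows this, and the earlier studies give no reason to expect it.

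No hypothesis is tested (SAP 5.1), and the primary PK analysis is unaffected.

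**What to change.** In SAP 6.6.2:
- replace the by-treatment summary of Period 2 Day 5 results with one overall column labelled 'after both formulations';
- show sequence and last treatment in the laboratory listing;
- show any early-termination or unscheduled results taken before dose 2 separately, by formulation received;
- state that the scheduled post-dose results cannot be attributed to a single formulation.

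The cost is SAP wording and laboratory table shells, with no change to visits or blood draws. Protocol 9.3.2 does not require laboratory tables by treatment and leaves table specifications to the SAP. Protocol 9 calls for an amendment only for major changes to the primary endpoint definitions or their analyses, so none is needed here. The downside is that the by-formulation laboratory columns are lost.
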